#### **10.1.1 Visit 1 (Week -4 ± 1, -35 days to -21 days)**

Following a discussion of participation in the clinical trial, informed consent must be obtained and documented. These steps precede any study procedures.

The following procedures will then be performed:

- Call IVRS/IWRS to assign patient number and register screening visit
- Interview to collect patient demographic information, asthma history (including smoking habits), other medical history and surgical history, and prior and concomitant medications
- Interview to collect vaccination information and vaccination plan during the treatment period for patient who agree to participate to the vaccine response assessment.
- Review entry criteria to assess eligibility, with special attention to verify the following:
  - Prescribed treatment dosage meets the pre-protocol definition of medium to high dose ICS ( $\geq 250$  mcg of fluticasone propionate twice daily or equipotent ICS daily dosage to a maximum of 2000 mcg/day of fluticasone propionate or equivalent) [Note for Japan: subjects aged 18 years and older, ICS must be  $\geq 200$  mcg of fluticasone propionate twice daily or equivalent; subjects aged 12 to 17 years, ICS must be  $\geq 100$  mcg of fluticasone propionate twice daily or equivalent] in combination with a second controller (eg, LABA, LTRA) for at least 3 months with a stable dose  $\geq 1$  month prior to Visit 1. In addition, patients requiring a third controller for their asthma are considered eligible for this study. The third controller should also be used for at least 3 months with a stable dose  $\geq 1$  month prior to Visit 1 (patients requiring systemic steroids as controller medication or biologics are excluded).
  - Patient has experienced, within 1 year prior to Visit 1: 1) Treatment with  $\geq 1$  systemic (oral or parenteral) steroids bursts for worsening asthma and/or 2) Hospitalization or an emergency/urgent medical care visit for worsening asthma.
- Measure vital signs [blood pressure, heart rate, respiration rate, body temperature, weight (kg), height (cm)]
- Perform physical examination
- Administer ACQ-7
  - Verify ACQ-5 score is  $\geq 1.5$
- Measure exhaled nitric oxide
  - Exhaled nitric oxide assessment is conducted prior to spirometry and following a fast of  $\geq 1$  hour.
- Perform spirometry
  - Entry criteria at Visit 1 include the requirement of a specific FEV1 and demonstration of reversibility as specified in Section 7.1. See below for additional directions.
  - Spirometry will be performed after a wash out period of bronchodilators according to their action duration, for example, withholding the last dose of salbutamol/albuterol or levosalbutamol/levalbuterol for at least 6 hours and withholding the last dose of LABA for at least 12 hours (ultra-long acting LABA like vilanterol should be withheld for at least 24 hours) and withholding the last dose of LAMA for at least 24 hours. This will be verified before performing the measurements.

- Pre-bronchodilator Forced expiratory volume (FEV1) must be  $\leq 80\%$  of predicted normal for adults and  $\leq 90\%$  of predicted normal for adolescents.
- Establish reversibility
  - Reversibility must be at least 12% and 200 mL in FEV1 after 200 mcg to 400 mcg albuterol/salbutamol or levalbuterol/levosalbutamol (2 to 4 inhalations of albuterol/salbutamol or levalbuterol/levosalbutamol, or of a nebulized solution of albuterol/salbutamol or levalbuterol/levosalbutamol, if considered as a standard office practice.
- Perform 12-lead electrocardiography (ECG)
- Perform chest X-ray or MRI (MRI is for Germany only) if no chest imaging (X-ray, CT, MRI) available within the previous 12 months as per local standard of care or if there is local requirement.
- Note for Japan: According to the request from the health authority, chest X-ray should be performed at screening visit if there is no chest imaging (Chest X-ray, CT, MRI) available within 3 months prior to screening to exclude patients with suspected active or untreated latent tuberculosis.
- Obtain (fasting if morning visit) blood samples for screening clinical laboratory determinations:
  - Hematology (see Section 9.2.2.5 for details)
  - Serum chemistry (see Section 9.2.2.5 for details)
- Obtain blood samples for hepatitis screen (HBs Ag, HBs Ab, HBc Ab including HBcAb IgM and total, and HCV Ab). In case of results showing HBs Ag (negative) and HBc Ab total (positive), a HBV DNA testing must be performed prior to randomization to determine eligibility. In case of results showing HCV Ab (positive), a HCV RNA testing must be performed prior to randomization to determine eligibility.
- Obtain blood sample for HIV screen (Anti-HIV-1 and HIV-2 antibodies)
- Obtain blood sample for ANA test. Note: Anti-ds DNA antibody will be tested if ANA is positive ( $\geq 1:160$  titer).
- Obtain blood sample for serum immunoglobulins (total IgG, IgG subclasses 1-4, IgM and IgA)
- Obtain serum  $\beta$ -HCG pregnancy test if female of childbearing potential
- Obtain urine for urinalysis (dipstick) If any assessment on the dipstick is abnormal, a urine sample should be sent to the central laboratory for testing.
- Dispense electronic diary/PEF meter, provide instructions for daily use, and remind patient to bring the device to the next visit.
- Remind patients to use salbutamol/albuterol or levosalbutamol/levalbuterol as reliever medication throughout the study. Instruct patient to record usage in the electronic diary.

- Remind patient to continue their stable dose of ICS in combination with one or two other controllers as used during the screening period and instruct patient to record daily usage in the electronic diary.
- Remind patient to withhold bronchodilators according to their action duration, for example, withhold last dose of salbutamol/albuterol or levosalbutamol/levalbuterol for at least 6 hours and withhold last dose of LABA for at least 12 hours (ultra-long acting LABA like vilanterol should be withheld for at least 24 hours) and withhold the last dose of LAMA for at least 24 hours prior to next visit.
- Schedule a site visit within 21 to 35 days (Visit 2, Week 0) and request patient to come at approximately the same time of this visit (fasting if morning visit).

#### 10.1.2 Visit 2 (Week 0, Day1)

- Record all medication use with start date and dose in eCRF; inquire about AEs/SAEs and background asthma therapy tolerability.
- Review entry criteria and reconfirm eligibility based on review of Inclusion/Exclusion Criteria.
- Administer ACQ-7 and all other scales (AQLQ(S), health care resource utilization questionnaire, EQ-5D-5L, SNOT-22 (only for those patients with bilateral nasal polyposis and/or chronic rhinosinusitis), RQLQ(S) +12 in those patients with allergic rhinitis and HADS (HADS-A and HADS-D subscales)). Verify ACQ-5 score is  $\geq 1.5$ .
- Compliance with use of the mandatory background therapy, ICS in combination with one or two other controller product as used just prior to screening, as defined as:
  - $\geq 80\%$  of total number of prescribed doses of background medication taken during the screening period. Compliance is verified based on background medication use recorded on the patient electronic diary during the screening period.
- Measure exhaled nitric oxide
  - Exhaled nitric oxide assessment is conducted prior to spirometry and following a fast of  $\geq 1$  hour.
- Measure vital signs (blood pressure, heart rate, respiration rate, body temperature, weight for all patients and height for adolescents only)
- Perform spirometry

Entry criteria at Visit 2 include the requirement of a specific FEV1 and demonstration of reversibility as specified in Section 7.1. See below for additional directions.

- Spirometry will be performed at approximately the same time of last visit after a wash out period of bronchodilators according to their action duration, for example, withholding the last dose of salbutamol/albuterol or levosalbutamol/levalbuterol for at least 6 hours and withholding the last dose of LABA for at least 12 hours (ultra-long acting LABA like vilanterol should be withheld for at least 24 hours) and withholding the last dose of LAMA for at least 24 hours and prior to administration of investigational product. This will be verified before performing the measurements.

- Pre-bronchodilator Forced expiratory volume (FEV1) must be ≤ 80% of predicted normal for adults and ≤ 90% of predicted normal for adolescents.
- Post-bronchodilator FEV1 should be determined
- Treatment Period stability limits will be established for FEV1 and PEF (The Treatment Period stability limit for PEF is defined as the respective mean AM or PM PEF obtained over the last 7 days prior to Day 1).

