## 4 INTRODUCTION AND RATIONALE

### 4.1 INTRODUCTION

Asthma is a chronic inflammatory disease of the airways characterized by airway hyperresponsiveness, acute and chronic bronchoconstriction, airway edema, and mucus plugging. The inflammatory component of asthma involves many cell types, including mast cells, eosinophils, T-lymphocytes, neutrophils, and epithelial cells and their biological products. For most asthma patients, a regimen of controller therapy and reliever therapy provides adequate long-term control. However, it is estimated that 5% to 10% of asthma patients have symptomatic disease despite maximum recommended treatment with combinations of anti-inflammatory and bronchodilator drugs. These patients account for up to 50% of the total health cost through hospital admissions, use of emergency services, and unscheduled physician visits (1).

The long term adverse effects of systemic and inhaled corticosteroids on bone metabolism, adrenal function, and growth in children lead to attempts to minimize the amount of corticosteroid usage. Additionally, the consequences of unresponsiveness to therapy or lack of compliance with therapy is loss of asthma control and ultimately, asthma exacerbation. The poor response of some patients with asthma may reflect the number of cellular and molecular mechanisms operative in asthma. There is increasing interest in distinct phenotypes because targeted therapy is more likely to be successful in patients with similar underlying pathobiologic features (2). Recent therapeutic approaches in asthma have been focused on trying to control the type 2 T-helper cell (Th2) response. Up-regulation of interleukin-4 (IL-4) and interleukin-13 (IL-13) activity has been implicated as an important inflammatory component of asthma disease progression. Dupilumab is under development as a potential novel treatment for asthma. Dupilumab, a fully human monoclonal antibody, is directed against the IL-4 receptor alpha subunit (IL-4R $\alpha$ ), which is a component of IL-4 receptors Type I and Type II, as well as the IL-13 receptor. The binding of dupilumab to IL-4R $\alpha$  results in blockade of downstream signaling initiated by both IL-4 and IL-13. For complete information regarding the preclinical and clinical evaluation of dupilumab to date, see the Investigator's Brochure.

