#### **4.2.1 Population rationale**

In this study, dupilumab will be added-on to an inhaled corticosteroid in combination with one or two other controller medications in patients with persistent asthma. The population is comprised of patients with a physician diagnosis of asthma for  $\geq 12$  months, based on the Global Initiative for Asthma (GINA) 2014 Guidelines (3) and entry criteria described in Section 7. As described above, in addition to suffering the symptoms associated with a lack of asthma control, such patients utilize a disproportionate level of health care services, may suffer the long term adverse effects of systemic and inhaled corticosteroids, and ultimately, are at increased risk of a severe asthma exacerbation.

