#### 9.2.1.1.3 *ACQ (Asthma Control Questionnaire)*

The ACQ was designed to measure both the adequacy of asthma control and change in asthma control which occurs either spontaneously or as a result of treatment.

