### **11.4.2 Analyses of efficacy endpoints**

#### ***11.4.2.1 Analysis of primary efficacy endpoints***

The annualized rate of severe exacerbation events will be analyzed using a negative binomial regression model. The model will include the total number of events occurring during the 52 weeks as the response variable, with the treatment group, age, region (pooled country), baseline eosinophil strata, baseline ICS dose level and number of severe exacerbation events within 1 year prior to the study as covariates. Log transformed treatment duration will be the offset variable. Patients who permanently discontinue the study medication will be asked and encouraged to return to the clinic for all remaining study visits and the additional off-treatment severe exacerbation events up to Week 52 will be included in the analysis and the last contact date at Week 52 will be used to calculate the offset variable.

The absolute change from baseline in FEV1 at Week 12 will be analyzed using a mixed-effect model with repeated measures (MMRM) approach. The model will include change from baseline in FEV1 values up to Week 12 as response variables, and treatment, age, sex, height, region (pooled country), baseline eosinophil strata, baseline ICS dose level, visit, treatment by-visit interaction, baseline FEV1 value and baseline-by-visit interaction as covariates. An unstructured correlation matrix will be used to model the within-patient errors. Parameters will be estimated using restricted maximum likelihood method with the Newton-Raphson algorithm. Statistical inferences on treatment comparisons for the change from baseline in FEV1 at Week 12 will be derived from the mixed-effect model. For patients discontinuing the treatment before Week 12, off study-treatment FEV1 values measured up to Week 12 will be included in the primary analysis.

Subgroup analyses will be performed for the two primary endpoints using the same methods by baseline eosinophil levels ( $\geq 300$  cells / $\mu$ L vs  $< 300$  cells / $\mu$ L and  $\geq 150$  cells / $\mu$ L vs  $< 150$  cells / $\mu$ L).

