The annualized rate of severe exacerbation events will be analyzed using a negative binomial regression model. The model will include the total number of events occurring during the observation period defined above as the response variable, with the four treatment groups, age, region (pooled country), baseline eosinophil strata, baseline ICS dose level and number of severe exacerbation events within 1 year prior to the study as covariates. Treatment groups, region, baseline eosinophil strata and baseline ICS dose level will be treated as categorical variable. Age and number of severe exacerbation events within 1 year prior to the study will be treated as continuous variable. Severe asthma exacerbation event prior to the study is defined as treatment with a systemic steroid (oral or parenteral) for worsening asthma at least once or hospitalization or emergency medical care visit for worsening asthma (as defined in section [Section 2.1.1](#)). Log transformed observation duration will be the offset variable.

Pairwise comparisons of the annualized event rates between each dose of dupilumab and its matching placebo will be derived by testing each dupilumab group versus its matching placebo separately. The estimated annualized event rate for each treatment group and its two-sided 95% confidence intervals will be derived from the negative binomial model. The event rate ratio of each dupilumab group and its matching placebo, two-sided 95% confidence interval of the rate ratio based on the negative binomial model and its p-value will be provided.

Based on EMEA feedback, the rate difference between each dupilumab group and its matching placebo, two-sided 95% confidence intervals of the rate difference and its p-value derived using delta method will also be provided as supportive information.

Sample SAS code can be found below:

```
proc glimmix data=event;  
  class eosblgpn ics trt01pn cntygrln;  
  model numevents=trt01pn age eosblgpn ics cntygrln asmanum  
    /offset=logdur dist=negbin link=log solution;  
run;
```

If the model fails to achieve convergence, different estimation algorithms will be applied following the order: default→LAPLACE→QUAD(8). If the issue still exists, other handling may be considered. The adjustment will be added to the footnote of the corresponding outputs.

The gross estimated of annualized events rate will also be presented by each treatment group. Mean cumulative function plot will be provided for descriptive purpose.

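### The primary exacerbation model does not adjust for baseline ACQ-5, a score already collected before randomization; if it is prognostic beyond the current covariates, adding it would tighten the rate ratios slightly

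*Protocol*

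**What the plan says.** **Model.** SAP 2.4.4.1.1 adjusts the negative binomial model for treatment group and for "age, region (pooled country), baseline eosinophil strata, baseline ICS dose level and number of severe exacerbation events within 1 year prior to the study". The sample code agrees: "model numevents=trt01pn age eosblgpn ics cntygrln asmanum". Protocol 11.4.2.1 has the same list, ending in "baseline ICS dose level and number of severe exacerbation events within 1 year prior to the study as covariates". ACQ-5 appears in none of them.

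**Collection.** Protocol 7.1 requires ACQ-5 of at least 1.5 at Visits 1 and 2. Protocol 10.1.2 has sites "Administer ACQ-7 and all other scales" at Visit 2, ahead of the randomization call. SAP 2.1.3 takes the last non-missing value up to randomization as baseline, so the Visit 1 score can stand in if the Visit 2 score is lost.

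**Rationale.** Protocol 9.2.1.1.3 states the instrument's purpose: "The ACQ was designed to measure both the adequacy of asthma control and change in asthma control". Protocol 4.1 describes the result of unresponsiveness or non-adherence to therapy as "loss of asthma control and ultimately, asthma exacerbation". Protocol 4.2.1 says that patients lacking control "ultimately, are at increased risk of a severe asthma exacerbation".

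**Present use for this endpoint.** SAP 2.4.4.1.1 lists ACQ-5 (≤2, >2) as a subgroup factor. The interaction model adds the dichotomized factor as a covariate, but the primary model does not use the score.

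**The concern.** A baseline variable that predicts the event count and is left out of a negative binomial model adds to the dispersion, which widens the interval for the rate ratio. With a log link, the treatment rate ratio keeps its meaning when such a covariate is added, so adjustment buys precision without changing the question.

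Of the covariates now in the model, the prior-year exacerbation count is history and ICS level is treatment intensity. None measures current control, which is what ACQ-5 scores.

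The stake is small for the first-ranked test, which is already very well powered. It is somewhat larger for the smaller rate comparisons in SAP Table 6: eosinophils ≥0.15, ≥0.3 and <0.3 Giga/L, and high-dose ICS. That table is one fixed sequence of 30 tests, so a miss ends formal testing. The <0.3 Giga/L rate test at 300 mg is step 10, and every 200 mg secondary test comes after it.

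**Working it through.** **Inputs from the documents** (Protocol 11.1, SAP 1.3): placebo rate 0.6, dupilumab rate 0.27 (ratio 0.45), dispersion k = 2, 546 vs 273 patients (ITT), 230 vs 115 (eosinophils ≥0.3 Giga/L), two-sided α = 0.05. Follow-up is taken as 1 year with no dropout.

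**Assumed inputs:** ACQ-5 SD 0.75; residual rate ratio per point r from 1.0 to 1.5, after the current covariates. The plan's k = 2 is taken as the dispersion without ACQ-5, because the documents do not say what it is conditional on.

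**Step 1. Reproduce the plan.**

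Var(log RR) = (1/0.6 + k)/n₀ + (1/0.27 + k)/n₁; power = Φ(|ln 0.45|/SE − 1.96).

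- ITT: 3.6667/273 + 5.7037/546 = 0.02388, so SE = 0.1545 and power is 99.9% (stated 99%).
- Eosinophils ≥0.3: 3.6667/115 + 5.7037/230 = 0.05668, so SE = 0.2381 and power is 91.8% (stated 91%).

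Both figures reproduce.

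**Step 2. Dispersion left after adjustment.** For an independent, roughly normal covariate, 1 + k = (1 + k′) × exp[(ln r × SD)²], so k′ = 3/exp[(ln r × 0.75)²] − 1.

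| r per point | k′ | ITT SE | SE reduction | ITT 95% CI at ratio 0.45 | Power, eosinophils ≥0.3 |
|---|---|---|---|---|---|
| 1.0 | 2.000 | 0.1545 | 0% | 0.332–0.609 | 91.8% |
| 1.2 | 1.944 | 0.1535 | 0.6% | 0.333–0.608 | 92.2% |
| 1.5 | 1.735 | 0.1497 | 3.1% | 0.336–0.603 | 93.3% |

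At r = 1.5 the variance ratio is 1.065, equivalent to about 6.5% more patients. ITT power stays above 99.9% throughout.

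**Step 3. Other Table 6 rate tests.** The documents give no power for these.

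- High-dose ICS, taking half of 1,638 (273 vs 136.5) at the plan's rates: 95.5%, rising to at most 96.5%.
- Eosinophils <0.3, taking the remaining 58% (about 316 vs 158), placebo rate 0.6 and k = 2: with an assumed 40% reduction, 74.2% rising to at most 77.0%; with an assumed 30% reduction, 45.7% rising to at most 48.4%.

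**Step 4. Sensitivity to the assumptions.** At r = 1.5, an SD of 0.6 to 1.0 gives an SE reduction of 2.0% to 5.4%. Reductions of 5.6% to 14.2% need the rate to double per ACQ-5 point.

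**Step 5. Simulation check.** With 300 trials per setting and an assumed skewed score floored at 1.5 (SD about 0.9 to 1.0), the mean SE without and with ACQ-5 was 0.1547 and 0.1548 (r = 1.0), 0.1535 and 0.1525 (1.25), and 0.1508 and 0.1468 (1.5). The mean log rate ratio moved by no more than 0.002 in these settings.

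**The case against.** **No documented gradient.** The rationale passages describe the enrolled population and the consequences of treatment failure. They do not say that, among patients all scoring 1.5 or more, a higher score means more exacerbations. Nor do they say that ACQ-5 adds anything once prior-year exacerbations, eosinophil stratum and ICS level are in the model. This stands. It makes the gain conditional and possibly zero, so a reader who concludes that the planned rate ratios are definitely less precise goes beyond the documents.

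**Reviewer preference.** The covariate list is prespecified, identical in both documents and includes the endpoint's own history. Other baseline measures, such as FEV1, FeNO and AQLQ, could also be proposed. This stands in part: it is why the point is an improvement and not a defect. ACQ-5 is distinguished by the protocol's link between control and exacerbation and by collection as an entry criterion.

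**Hospitalization and emergency-room events.** A reader might expect this test to benefit as well. These events are a subset of severe exacerbations, so their rate is lower and 1/μ dominates the variance. Keeping k = 2, r = 1.5 and SD 0.75, the SE reduction is 2.0% at half the planned rates, 1.2% at a quarter and 0.5% at a tenth (the lower rates are assumed). The objection holds, and no benefit is claimed there.

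**Cox models.** Extending the change to time to first event might also seem natural. Hazard ratios are non-collapsible, so adding a covariate alters what is estimated. That change is not recommended on these grounds.

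**Completeness.** ITT includes anyone randomized, and SAP 2.2.1 foresees ineligible patients being randomized. A few scores could be missing, although the last-non-missing rule limits this.

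**Conclusion.** The point holds as an optional, low-cost improvement. The primary exacerbation model omits a baseline score that is available for every eligible patient and that the protocol's reasoning makes a plausible predictor. Under the assumed SD of 0.75 and a rate ratio of 1.0 to 1.5 per point, adjustment lowers the ITT standard error by 0% to about 3% and raises eosinophil ≥0.3 power by at most about 1.5 percentage points. All of this rests on an SD and an adjusted association that the documents do not supply.

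A reader might infer that the primary comparison is biased, underpowered or open to a false positive. The documents do not support that: the omission does not bias the rate ratio or affect type I error, and planned ITT power reproduces at above 99%. Nor is ACQ-5 ignored for this endpoint, since it is a prespecified subgroup factor.

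**What to change.** Before database lock and unblinding, add continuous baseline ACQ-5 (last non-missing value up to randomization) to the severe-exacerbation negative binomial model in SAP 2.4.4.1.1. Apply it to the ITT analysis and to the eosinophil-subgroup and high-dose-ICS rate tests in Table 6, and align Protocol 11.4.2.1. Keep the current covariate set as a sensitivity analysis, and state how a missing baseline score would be handled. Leave the hospitalization/emergency-room rate model and the Cox models unchanged.

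The sponsor could first check the adjusted association in its 776-patient dose-ranging study (Protocol 4.2.4), if baseline ACQ-5 was recorded there. The cost is one SAP edit and one degree of freedom, with no new data or patients.
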